3.4.3.4. Data collection

Baseline and endline KIIs with province and district authorities and FGDs with health center staff, VMWs, and high-risk populations (HRPs) will be conducted to qualitatively assess the feasibility, acceptability and safety of community-based RACD practices, including G6PD deficiency and primaquine knowledge, attitudes, and practices. The outputs of a process-mapping workshop and co-design workshop at two purposively selected health facilities will be documented and used to inform downstream training materials and counselling messages.

Standardized tools including interview/discussion guides and a competency checklist will be developed using best practices in qualitative research, and translated and back-translated prior to implementation. Study staff and an independent FGD/KII moderator will be trained on the appropriate tools, and all interviews will be conducted in the local language. The end-line FGDs and KIIs will explore constraints and any issues related to all the topics identified from the quantitative survey, field experience implementing the RACD intervention, and barriers to implementation of malaria control efforts. Informed consent will be obtained from all FGD, KII, and HRP participants in the local language prior to any data collection. FGDs and KIIs will be audio-recorded, transcribed, and the transcripts translated into English.

Themes to be explored during the KIIs and FGDs include the following: Demographics of HRP groups; Occupations of HRP groups, including seasonality of work; Forest-going behaviors; Migratory patterns; Health-seeking patterns and behaviors; Social networks and congregation/frequented sites (locations and days/times visited); Ideal locations and times to access HRPs for case management and surveillance activities; Operational feasibility and attitudes towards VMW-led active case detection; Capacity to conduct active case detection in forest workers; Knowledge, attitudes, and practices related to *P. vivax* infection, G6PDd testing, and primaquine.

FGDs and KIIs will be grouped as follows:

- 1) High risk populations (HRPs), including recent malaria cases who have worked or traveled at least one night at a forest or forest-fringe site located outside of a permanent settlement in the past 30 days
- 2) Health facility-based staff involved in malaria diagnosis and treatment
- 3) Village Malaria Workers and other community members
- 4) Provincial and district health officers
- 5) Other health sector and ministry personnel
- 6) Process-mapping and co-design workshops. Participation will include a cross-section of supervisors, health center staff, VMWs, and community members at 2 health centers. The health centers will be purposively selected based on malaria case volume.

At endline, FGDs and KIIs will be conducted with health center staff, VMWs, and HRPs. Themes to be explored during KIIs and FGDs include: Forest-going behaviors; Migratory patterns; Health-seeking patterns and behaviors; Operational feasibility and attitudes towards VMW-led active case detection; Capacity to conduct active case detection in forest workers; Knowledge, attitudes, and practices related to *P. vivax* infection, G6PDd testing, and primaquine; Facilitating factors and challenges to scale-up of the interventions.

These KIIs, FGDs and participatory research methods will focus on assessing the operational feasibility and acceptability of community-based active case detection in both villages and forest workers, G6PDd referral, and treatment follow-up of radical cure for *P. vivax* infection using 14-day primaquine.

The costs of RACD will be collected. Total costs as a unit as well as cost-effectiveness will be assessed as an incremental cost effectiveness ratio (ICER). The types and potential sources of expenditure data are shown in Table 6.

Table 6. Types and potential sources of expenditures

Expenditure category	Types of expenditure needed	Potential sources of information
Personnel	All human resource expenditures and time contributions 
 • Salary/wage payments • Value of benefits • Volunteer labor 	
 • Annual program budgets for salaries and benefits • Work logs or reports from volunteers
Commodities and Services	All supplies and services used toward RACD activities 
 • In-kind donations • Purchased commodities (including acquisition costs) • Utilities • Travel/transit costs: fuel, transit fees and services, airfare • Reproduction costs, postage • Staff trainings: per diem payments, trainer fees, consultants • Current rental value of property 	
 • Printing and postage receipts • Training budgets and receipts • Vehicle travel logs, fuel receipts • Utility bills • Consultant invoices

Focus groups will be facilitated by two members of the research staff: 1 moderator and 1 note-taker. A locally-appropriate location will be used to hold the focus group discussions (i.e., community center, health facility, etc). After a brief introduction, the moderator will obtain informed consent separately from each participant. All sessions will be audio recorded. During the sessions, the research staff will generate notes as the discussion unfolds to help formulate follow-up questions and probes, with no identifying information.

For interviews and focus groups, the note taker and moderator will discuss interview notes/similarities, and responses will be recorded/finalized at the end of each interview. The moderator for each group will transcribe the recording and once all focus groups have been conducted and data transcribed, and results disseminated, all audio recordings will be destroyed. A professional translator will translate the transcript to English. The local study coordinator will supervise and review the local language and English transcripts to ensure accuracy. Each focus group discussion will take approximately 1-2 hours total and occur at an appropriate time for the study respondents (i.e., weekday vs weekend; morning vs afternoon).

Data from the interviews and focus groups will be entered into Dedoose or a similar program for simple thematic analysis and stored on a password protected device. All data will be stored on a password-protected database and will only be available to the study personnel. All data from participants will be coded using a study identification number in place of the individual's name. Data will be analyzed to provide preliminary descriptive statistics on the study population and recurrent themes within the assessment. Data will only be used for the purposes of this study.

All participants will receive locally-appropriate compensation for participating in the focus group or interview to compensate for travel costs and time, and will be determined following discussions with

local partners. Light snacks and non-alcoholic refreshments will be provided during the focus group session.

3.4.3.5. Analytical plan

Outcome 1: Village-based population coverage of test and treat interventions

The operational coverage will be estimated at the individual and household level as the percent of the population that received a visit from the intervention teams to offer the RACD intervention, among those eligible for inclusion. This will be obtained from a combination of RACD program data and enumeration data. Additionally, the proportion of individuals accepting the RACD interventions, among those eligible for inclusion in the intervention, will be estimated, providing an estimate of the effect coverage of each program. Data for the denominator of individuals and households targeted for the intervention will be ascertained from the household enumeration for the sampling frame. Additionally, to validate the enumeration, attempts will be made to use remote sensing data, and/or Google Earth, to enumerate household structures. To the extent possible, individual, household and community level factors associated with coverage will be assessed using mixed effects logistic regression.

Outcome 2: Feasibility of conducting RACD interventions

The operational feasibility of VMWs to conduct RACD interventions will be estimated at the individual level as the percent of VMWs and health center staff who rate the intervention activities as very easy, somewhat easy, somewhat difficult, and very difficult. Supervisors will conduct a competency checklist on 2 VMWs per intervention area (32 total) at baseline, midline, and end-line; the capacity of following case investigation, recording, management, and follow-up SOPs will be assessed over time. Qualitative surveys will be conducted with VMWs and health center staff at endline. The costs of RACD and cost-effectiveness will be assessed as an incremental cost effectiveness ratio (ICER). Program data on costs/expenditure for RACD will be collected and combined with estimates of program effectiveness to determine ICER.

Outcome 3: Acceptability of community-based RACD approaches

The acceptability of a community-based approach for RACD will be assessed as the proportion of targeted individuals refusing RACD intervention, among those eligible for inclusion. Qualitative data collection methods such as focus groups and key informant interviews with villagers, forest workers, VMWs and other health sector staff will be implemented.

Outcome 4: Safety of community-based RACD and treatment follow-up

The adverse event rate for RDT positive participants will be assessed using intervention data and health facility adverse event reporting forms. Study staff and VMWs will be trained on detection of adverse events for positive cases receiving treatment.

Outcome 5: Operational feasibility of G6PD referral, testing and non-adherence

The operational feasibility of G6PD referral, testing and non-adherence at the community and facility levels will be evaluated. For testing, interview data at baseline and endline will be collected from district health staff and community members, as well as focus group discussions with both groups at end-line. Risk factors for non-adherence to G6PD testing after referral will be determined through comparison of factors captured at enrollment for individuals who were tested at a facility versus those who were not.

Outcome 6: Assessment of *P. vivax* treatment adherence

The treatment adherence of *P. vivax* positive study participants will be assessed through physical evidence of adherence during VMW follow-up visits on day 3, 7 and 14 and comparison of relapse rates across study arms.

3.4.4. Assessment of the risk of malaria vector biting in forest and village settings

A baseline entomological investigation will be conducted along with the baseline qualitative activities in Aug/Sep 2019. The investigation will involve collection of vector occurrence and density data (by species), human landing catches (HLC) to assess vector biting behaviors (indoor vs outdoor and forest sites), and household structure type, and human behavioral observations. All collections will take place over a one-week period. HLC collections will occur in 4-5 sleeping structures each in the forest and village, with 2 HLC collectors by structure. At the end of each HLC collection hour, collectors will also record human behavior (sleeping (or awake) under net/sleeping without net/awake), both indoors and outdoors. Field collectors will be community volunteers that will have been properly informed about the sampling methods and their implications, and who have consented to participating by signing consent forms. Prior to the start of collections, volunteers will also need to be tested for malaria. Depending on national policy, they may also be required to take malaria prophylaxis. HLC data collection forms are found in the Appendix.

4 Ethical issues related to human subjects research

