- a. Peer referrals will be screened for eligibility by the VMW and, if eligible, informed consent will be conducted in the appropriate local language.
- b. Consenting referrals will provide a fingerstick blood sample for testing with the HS-RDT, standard combination RDT and four blood spots on filter paper. If infection is present according to any RDT, they will receive treatment following the guidelines in the following section.
- c. All consenting referrals will complete an interviewer-administered survey questionnaire.

For VB-RACD, if available, employers will be contacted by the VMW to coordinate a potential visit to identified work sites.

- a. Work sites considered for VB-RACD will meet the following criteria:
 - Case reports that the work site is currently active
 - Case reports there are at least five other workers who work or sleep there (the minimum threshold ensures that screening there is worthwhile, given logistic constraints, and will be specified in SOP)
 - The work site is safe to visit and accessible
 - The nearest VMW has necessary permissions to travel to site

- b. The nearest VMW will travel to any such work sites identified
- c. All workers present at the site(s) will be screened for eligibility and, if eligible, informed consent will be conducted.
- d. Consenting referrals will provide a finger stick blood sample for testing with the HS-RDT, standard combination RDT, and four blood spots on filter paper. If infection is present according to any RDT they will receive treatment following the guidelines in the following section.
- e. All consenting referrals will complete an interviewer-administered survey questionnaire.

All participants will receive a small token of participation such as a bar of soap or phone credit.

Forest workers may be difficult to reach at their places of residence as they are often away from the household. When following-up with PR-RACD referrals, VMWs will attempt to contact them directly by phone multiple times and visit the household if the address was provided or they are familiar with the location. When referrals are unreachable by phone or the residential location is unknown, VMWs will elicit the help of the village leader to identify where they live or how best to contact them. VMWs will record each contact into a register of all individuals in their community known to travel to forest, the location of their residence, and location of work-site if possible.

Case Management and Follow-up

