3.4. Study evaluation methods

3.4.1. Overview of evaluation activities by study objectives, outcomes, and data collection activities

Table 4. Overview of evaluation activities

Study activity	Research objective	Primary outcome measures	Data collection activity
Activity 1: Impact evaluation of enhanced RACD	1. Evaluate the relative effectiveness of enhanced community-based RACD using HS-	Total confirmed outpatient (OPD) P. falciparum and P. vivax malaria case incidence among all ages by health facility catchment	Routine malaria data from all reporting VMWs, health centers and district hospitals

	RDTs in villages and forest-based HRPs, compared to control	P. falciparum and P. vivax prevalence in all individuals	Cross-sectional parasite survey November-December 2020	
		HS-RDT and RDT test positivity rate	HS-RDT and RDT positivity data from RACD intervention data	
Activity 2: Assessment of the feasibility and acceptability of community-based RACD	1. Assess the operational feasibility of community-based RACD	Population coverage of RACD and interventions	RACD intervention data	
		Proportion of VMWs who rate conducting the RACD interventions as very easy, somewhat easy, somewhat difficult, and very difficult, and changes in proportions over time	Entrance, mid-intervention, and exit competency checklists with VMWs; focus group discussion and interviews with VMWs at end-line	
		Costs of RACD as unit and total costs; cost-effectiveness will be assessed as an incremental cost effectiveness ratio (ICER)	Program data on costs combined with estimates of program effectiveness	
	2. Assess the acceptability of community-based RACD	Proportion of targeted individuals refusing RACD intervention	RACD intervention data	
		Proportion of survey respondents who strongly disagree, disagree, are ambivalent, agree and strongly agree on the importance and acceptability of community-based RACD	Cross-sectional survey and qualitative studies at endline with villagers, forest workers, VMWs and other health sector staff	

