3.4.3.2. Primary outcomes measures

1. Population coverage of enhanced RACD interventions: this indicator will be measured in two ways. Operational program coverage will be defined as the proportion of individuals ≥ 18 months old and households visited and offered the RACD interventions within the target areas per time period. Effective program coverage is defined as the proportion of individuals (≥ 18 months old) that agreed to participate in the RACD intervention among all individuals ≥ 18 months old eligible to participate in the intervention in the target population per time period.
2. Feasibility of conducting enhanced RACD intervention at the community level: feasibility will be determined based upon a combination of population coverage data, responses of provincial, district, and health staff, VMWs, and community members to KIIs and FGDs at baseline and endline, VMW competency checklists at baseline, midline, and endline, and cost data.
3. Acceptability of community-based RACD approaches: acceptability will be determined based upon refusal rates during interventions and responses of community members and VMWs to endline questionnaire, interviews, and focus groups.
4. Safety of community-based RACD and treatment follow-up: safety measures will include the adverse event rate amongst treated individuals and hemoglobin measurement pre and post treatment for individuals receiving PQ.
5. Operational feasibility of G6PD referral: operational feasibility of G6PD referral will be determined by the results of the process-mapping and co-design workshops at baseline, responses of health staff and VMWs to interviews and focus groups at baseline and endline and competency checklists at baseline, midline, and endline, the proportion of referred *P. vivax* cases presenting at a health facility for G6PD testing, and the proportion of *P. vivax* cases with a valid recorded G6PD result.
6. Assessment of *P. vivax* treatment adherence: treatment adherence will be determined by the proportion of *P. vivax* cases with physical evidence of adherence through pill count, the *P. vivax* relapse rate across study arms, and the proportion of *P. vivax* cases with successful parasite clearance on day 14.

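### The refusal measure of acceptability divides by everyone eligible, not by those offered RACD, so it mixes non-contact with acceptance and understates refusal wherever contact is incomplete

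*Protocol*

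**What the plan says.** The Protocol words the refusal measure in three places.

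- Section 3.4.3.5, Outcome 3: acceptability "will be assessed as the proportion of targeted individuals refusing RACD intervention, among those eligible for inclusion".
- The overview table of evaluation activities in section 3.4.1: "Proportion of targeted individuals refusing RACD intervention", taken from RACD intervention data.
- Section 3.4.3.2, item 3: "acceptability will be determined based upon refusal rates during interventions", with no denominator given.

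Two statements under Outcome 1 of section 3.4.3.5 show who is in the eligible or targeted group. Operational coverage is the "percent of the population that received a visit from the intervention teams to offer the RACD intervention, among those eligible for inclusion". The source of the targeted group is also fixed: "Data for the denominator of individuals and households targeted for the intervention will be ascertained from the household enumeration for the sampling frame".

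Section 3.4.3.2, item 1, keeps being offered RACD apart from being eligible for it. Operational coverage there concerns individuals and "households visited and offered the RACD interventions within the target areas per time period", while effective coverage counts those who agreed among all who were eligible.

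**The concern.** A person who was away from home or could not be traced had no opportunity to refuse. If that person stays in the denominator, non-contact is counted as non-refusal.

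Incomplete contact is to be expected under the procedures in section 3.3.1. An absent household member is revisited only if recent fever is reported for an absent member or someone else in the household tests positive, so other absent residents may never receive an offer. For peer referrals the protocol itself warns: "Forest workers may be difficult to reach at their places of residence as they are often away from the household".

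Acceptability in village and forest working populations is part of secondary objective 1, and the refusal share is its main quantitative measure from the intervention itself. As defined, a strategy that reaches fewer people can show a lower refusal figure with no difference in how willing people are.

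**Working it through.** The protocol states no contact rate, refusal rate or acceptability figure for RACD, so there is no figure of its own to reproduce. The rates below are assumptions, shown over a range.

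**Step 1. Who is in the denominator.** Outcome 1 divides those visited by those eligible. If eligible meant only people already visited, that ratio would always be 100%. In that section, then, eligible includes people not visited. Outcome 3 uses the same phrase for its denominator.

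**Step 2. What the measure equals.** Let c be the share of eligible people contacted and offered RACD, and r the share refusing among those offered.

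- Measure as written: refusers / eligible = c × r
- Refusal among those offered: refusers / offered = r

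**Step 3. Size over a range of assumed values.**

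| Assumed r | c = 90% | c = 50% | c = 30% | Offered denominator |
|---|---|---|---|---|
| 5% | 4.5% | 2.5% | 1.5% | 5% |
| 10% | 9.0% | 5.0% | 3.0% | 10% |
| 20% | 18.0% | 10.0% | 6.0% | 20% |

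The understatement is (1 − c) of the true value: a tenth at 90% contact, half at 50%.

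**Step 4. Does this settle a village and forest ordering?** It does not. Take village c = 90% and r = 10%, which reads 9.0%.

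- Forest c = 50%, r = 10%: 0.50 × 0.10 = 5.0%, so forest looks lower.
- Forest c = 50%, r = 18%: 0.50 × 0.18 = 9.0%, a tie.
- Forest c = 50%, r = 20%: 0.50 × 0.20 = 10.0%, so forest looks higher.
- Forest workers counted as eligible only once contacted, r = 10%: the figure is 10%, above the village 9.0% although true refusal is the same.

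**Step 5. Can r be recovered from what is planned?** If operational coverage (c) and effective coverage (c × (1 − r)) share one eligible denominator, then r = 1 − effective / operational. With c = 50% and r = 10%, effective coverage is 45%, and 1 − 45/50 = 10%. This works where both coverages exist for the same group. It is not assured for forest workers, because Outcome 1 is headed "Village-based population coverage of test and treat interventions" and its denominator comes from household enumeration.

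**The case against.** The strongest reply is that the rest of the plan largely protects the reader. Operational and effective coverage are both to be reported, so low reach would be visible beside the refusal figure and Step 5 could be applied. Section 3.4.3.2 defines coverage without limiting it to villages, and its wording of refusal is compatible with an offered denominator. Acceptability also draws on endline survey ratings, focus groups and interviews. The measure is descriptive, with no hypothesis test attached. All of this stands and limits the harm. It does not change the definition that the analysis section fixes, and the result labelled as refusal would still be c × r.

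A second reply is that the inclusion criteria in section 3.2 require participants to be willing and available, so that unreached people are not eligible at all. Read literally, the same criterion removes refusers too and makes refusal zero by construction. It shows that eligible is used inconsistently and does not rescue the measure.

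A reader might go further and infer that forest workers, as the hardest group to reach, would appear the most accepting. The documents do not support that:

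- Section 3.3.1 screens peer referrals for eligibility at contact and, at work sites, screens only the workers who are present. Eligible forest workers may thus be mostly people already reached.
- Household enumeration may leave out co-workers met at sites. Those who are not in the denominator cannot dilute it. Peer referrals resident in the village may be listed.
- No village-versus-forest comparison of refusal is specified.
- The ordering depends on contact and refusal rates that the protocol does not give (Step 4).

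**Conclusion.** The point holds as a defect of definition. The refusal share in section 3.4.3.5 counts people who were never offered RACD as non-refusers, so it equals the contact rate times true refusal and understates refusal whenever contact is incomplete. On assumed values, 10% true refusal reads as 9%, 5% or 3% at 90%, 50% or 30% contact. The direction of the bias follows from the wording; its size rests on contact rates that the documents do not give.

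The effect is clearest for absent household members who are not revisited, and it may extend to untraced peer referrals. The direction of any difference between villagers and forest workers is not established. The primary outcomes are untouched. The change is worth making because the measure serves a stated secondary objective and the correction is nearly free.

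**What to change.** 1. In section 3.4.3.5, Outcome 3, and in the overview table in section 3.4.1, define refusal as persons declining divided by persons contacted and offered RACD. Give section 3.4.3.2, item 3, the same denominator.
2. Report non-contact as a separate measure, and show refusal and non-contact for household, peer-referral and venue-based RACD.
3. For peer-referral reach, use the peers named by the index case as the denominator. For venue-based RACD, workers present at visited sites can serve as the offered denominator for refusal. They cannot measure reach, because they have already been found, so the report should say that missed workers are not captured.
4. Reconcile the meaning of eligible across the inclusion criteria in section 3.2, the coverage definitions in section 3.4.3.2 and the analysis in section 3.4.3.5, so that refusers are not excluded from their own denominator.

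The cost is a few changes of definition. The peer lists, VMW contact registers and site screening are already part of the procedures in section 3.3.1. The downside is a less favourable refusal figure.
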